Title Safety and Immunogenicity Study of GSK Meningococcal Group B Vaccine *Bexsero* (GSK3536829A) when Administered Concomitantly with GSK Meningococcal MenACWY Conjugate Vaccine *Menveo* (GSK3536820A) to Healthy Subjects 16-18 Years of Age.

Investigator name

Signature

Date

Sponsor Information

1. Sponsor

GlaxoSmithKline Biologicals SA
[name]

2. Sponsor Medical Expert for the Study

Refer to the local study contact information document.

3. Sponsor Study Monitor

Refer to the local study contact information document.

4. Sponsor Study Contact for Reporting of a Serious Adverse Event

GSK Biologicals Central Back-up Study Contact for Reporting SAEs: refer to protocol Section [12.5.9.3](#).

GSK Biologicals Central Safety Physician and Back-up Phone contact: refer to protocol Section [8.4.6.1](#).

PROTOCOL AMENDMENT 7 SUMMARY OF CHANGES TABLE

Table 1 Document history

Document	Date
Protocol Amendment 7	11 October 2022
Protocol Amendment 6	21 June 2022
Protocol Amendment 5	13 April 2021
Protocol Amendment 4	26 November 2020
Protocol Amendment 3	29 September 2020
Protocol Amendment 2	23 January 2020
Protocol Amendment 1	14 August 2019
Original Protocol	28 June 2016

Amendment 7: 11 October 2022

Overall Rationale for the Amendment change

The purpose of the amendment 7 is to shorten the safety follow-up period to 6 months in subjects who have not reached the 6-month safety follow-up after the last dose, at the time this amendment takes effect, as the comprehensive safety data in this population indicates that the safety of the trial participants is not jeopardized and does not pose any meaningful threat. These data include all previous pivotal clinical studies, the recently completed V72_72 study in the same population and post-marketing experience in countries where *Menveo* and *Bexsero* are marketed, and in majority of cases are given concomitantly.

The purpose of this amendment is also to extend the visit window to 28 days post reference day to mitigate the impact of COVID pandemic, including quarantine, mandatory vaccination, or other disturbances in the study procedures.

Table 2 List of main changes in the protocol and their rationale

Section # and Name	Description of Change	Brief Rationale
Contributing authors	Updated job titles	Internal update in name of job titles
Sponsor signatory page	Updated job title	Internal update in name of job title
Section 1	Updated objectives and endpoints table Updated overall design figure Updated text	To incorporate 2 additional primary endpoints To incorporate a shortened safety follow-up into the overall design figure To introduce a shortened safety follow-up period in subjects who have not reached safety follow-up (SFU) 5 (Day 271) at the time this amendment takes effect
Table 3	Added a bullet mark for study conclusion also under SFU 5 and added a footnote with details	To introduce a shortened safety follow-up period in subjects who have not reached SFU 5 (Day 271) at the time this amendment takes effect
Table 4	Updated	To extend the visit window to 28 days post reference day
Table 5	Addition of footnote	To introduce a shortened safety follow-up period in subjects who have not reached

CONFIDENTIAL

205419 (MENB REC 2ND GEN-045 (V72_79))

Protocol Amendment 7 Final

Section # and Name	Description of Change	Brief Rationale
		SFU 5 (Day 271) at the time this amendment takes effect
Table 6	Updated	To incorporate 2 additional primary endpoints
Figure 1	Updated	To introduce a shortened safety follow-up period in subjects who have not reached SFU 5 (Day 271) at the time this amendment takes effect
Section 5.2 Section 5.4 Section 7.5.1 Section 8.4.3 Section 8.6 Section 12.5.8	Addition of text	To introduce a shortened safety follow-up period in subjects who have not reached SFU 5 (Day 271) at the time this amendment takes effect
Table 14	Table revised	To provide clarity on what assay to be performed at which visit.
Table 15	Table title edited	To clarify that study conclusion at Day 451 is applicable in subjects who have crossed Day 271
Table 16	New table created	To clarify that study conclusion at Day 271 is applicable in subjects who have not reached Day 271

TABLE OF CONTENTS

	PAGE
SPONSOR INFORMATION	7
1. SYNOPSIS.....	18
2. SCHEDULE OF ACTIVITIES (SOA).....	24
3. INTRODUCTION.....	27
3.1. Study rationale.....	27
3.2. Background	27
3.3. Benefit/Risk assessment.....	29
3.3.1. Risk assessment.....	30
3.3.2. Benefit assessment	32
3.3.3. Overall Benefit: Risk conclusion.....	32
4. OBJECTIVE(S) AND ENDPOINT(S).....	32
5. STUDY DESIGN	35
5.1. Scientific rationale for study design.....	35
5.1.1. Rationale for the use of placebo	36
5.2. Overall design (Amended 11 October 2022)	36
5.3. Number of subjects.....	39
5.4. Subject and study completion	39
6. STUDY POPULATION	40
6.1. Inclusion criteria for enrolment.....	40
6.2. Exclusion criteria for enrolment.....	41

1. SYNOPSIS

Indication:

Active immunization against invasive disease caused by *N. meningitidis* serogroup B strains. Although the meningococcal group B vaccine was developed for individuals aged 2 months and older, the actual age range for which this recommendation extends varies depending on the approval from different health authorities. In the US, the current indication is for individuals 10 through 25 years of age.

Rationale:

- Rationale for the study

Data from clinical studies conducted in several age groups show that rMenB+OMV NZ and MenACWY are well tolerated and immunogenic when administered with a number of other vaccine antigens, including Diphtheria, Tetanus and acellular Pertussis (DTPa). Data from an infant study showed that both rMenB+OMV NZ and MenACWY were well tolerated and immunogenic when administered concomitantly in healthy infants. No data is currently available on the concomitant use of rMenB+OMV NZ and MenACWY in adolescents.

The purpose of this clinical study is to evaluate the immunogenicity, the safety, and the tolerability of rMenB+OMV NZ and MenACWY vaccines when concomitantly administered to healthy subjects 16-18 years of age.

- Rationale for the study design

The purpose of this study is to assess the safety and demonstrate the non-inferiority of the antibody responses of rMenB+OMV NZ and MenACWY vaccines when concomitantly administered compared to either alone in healthy subjects 16-18 years of age. The subjects will be randomized to one of the 3 parallel treatment arms in a 1:1:1 ratio to receive the concomitant rMenB+OMV NZ and MenACWY vaccines (Group MenB+MenACWY) or rMenB+OMV NZ vaccine + placebo (Group MenB) or MenACWY vaccine+ placebo (Group MenACWY) in 2 different arms.

- Rationale for the use of placebo

In order to ensure proper blinding, placebo will be administered to subjects in all groups in a staggered fashion. Subjects in Group MenB and Group MenACWY will be administered Placebo at Visit 1 and for subjects in Group MenB+MenACWY, placebo will be administered at Visit 4 (study Day 91).

Objectives and Endpoints (Amended 11 October 2022):

Objectives	Endpoints
Primary	

To assess the safety and tolerability of rMenB+OMV NZ and MenACWY, when administered concomitantly or alone, in healthy subjects 16-18 years of age.
	
 The frequencies and percentages of subjects with solicited local (i.e., injection site pain, erythema, swelling, induration) and systemic (i.e., fever [temperature $\geq 38.0^{\circ}\text{C}/100.4^{\circ}\text{F}$], nausea, fatigue, myalgia, arthralgia, headache) adverse events (AEs) during the 7 days (including the day of vaccination) following the first (Visit 1, Day 1/Month 0), the second (Visit 3, Month 2) and the third (Visit 4, Month 3) vaccination for all groups. The frequencies and percentages of subjects with any unsolicited AEs (including all SAEs), AEs leading to withdrawal and medically attended AEs during the 30 days (including the day of vaccination) following the first (Visit 1, Day 1/Month 0), the second (Visit 3, Month 2) and the third (Visit 4, Month 3) vaccination for all groups. The frequencies and percentages of subjects with SAEs, AEs leading to withdrawal, and medically attended AEs, throughout the study period (Day 1/Month 0 to Month 9). The frequencies and percentages of subjects (who received rMenB+OMV NZ) with AESI throughout the study period (Day 1/Month 0 to Month 9). Among subjects who are followed for 12 months after their last dose: 
 The frequencies and percentages of subjects with SAEs, AEs leading to withdrawal, between SFU 5/Month 9 and SFU 7/Month 15. The frequencies and percentages of subjects (who received rMenB+OMV NZ) with AESI between SFU 5/Month 9 and SFU 7/Month 15.

To demonstrate the non-inferiority of the antibody response to rMenB+OMV NZ given concomitantly with MenACWY to healthy subjects 16-18 years of age compared to rMenB+OMV NZ administered alone, as measured by serum bactericidal assay using human complement (hSBA) Geometric Mean Titers (GMTs) against N. meningitidis serogroup B indicator strains M14459 (fHbp), 96217 (NadA), NZ98/254 (PorA) and M07-0241084* (NHBA), at one month after the second vaccination with rMenB+OMV NZ.
 
Criterion: Non-inferiority will be demonstrated if for each of the four serogroup B test strains, the lower limit of the 2-sided 95% confidence interval of the between-group ratio of hSBA GMTs (rMenB+OMV NZ with MenACWY versus rMenB+OMV NZ alone) is >0.5.
	
 Co-primary endpoints for Group MenB+MenACWY and Group MenB are the hSBA GMTs for rMenB+OMV NZ against each of the four serogroup B test strains (M14459, 96217, NZ98/254 and M07-0241084) at one month after the second vaccination with rMenB+OMV NZ (Visit 4, Month 3).

CONFIDENTIAL

205419 (MENB REC 2ND GEN-045 (V72_79))

Protocol Amendment 7 Final

Objectives	Endpoints

To demonstrate the non-inferiority of the antibody response to MenACWY given concomitantly with rMenB+OMV NZ to healthy subjects 16-18 years of age compared to MenACWY administered alone, as measured by hSBA GMTs against each of the N. meningitidis serogroups A, C, W and Y, at one month after the (study) vaccination with MenACWY.
 
Criterion: Non-inferiority will be demonstrated if for each of the four serogroups A, C, W and Y, the lower limit of the 2-sided 95% confidence interval of the between-group ratio of hSBA GMTs (rMenB+OMV NZ with MenACWY versus MenACWY alone) is >0.5.
	
 Co-primary endpoints for Group MenB+MenACWY and Group MenACWY are the hSBA GMTs against each of the four serogroups A, C, W and Y with MenACWY at one month after the study vaccination of MenACWY (Visit 2, Month 1).
Secondary	

To assess the non-inferiority of the responses to MenACWY when given concomitantly with rMenB+OMV NZ to healthy subjects 16-18 years of age compared to MenACWY administered alone as measured by Enzyme-Linked Immunosorbent Assay (ELISA) Geometric Mean Concentrations (GMCs) against each of the serogroups A, C, W and Y, at one month after the (study) vaccination with MenACWY.
 
Criterion: Non-inferiority will be demonstrated if for each of the four A, C, W and Y strains, the lower limit of the 2-sided 95% confidence interval of the between-group ratio of ELISA GMCs (MenACWY with rMenB+OMV NZ versus MenACWY alone) is >0.5.
	
Immune response to MenACWY The immune response to MenACWY when administered with/without rMenB+OMV NZ at one month after the first vaccination (Visit 2, Month 1; Groups MenB+MenACWY and MenACWY) will be assessed for the serogroups A, C, W and Y as ELISA GMCs.


To assess the immune response to rMenB+OMV NZ in healthy subjects 16-18 years of age against N. meningitidis serogroup B test strains M14459 (fHbp), 96217 (NadA), NZ98/254 (PorA) and M07-0241084* (NHBA), at one month after the first and the second vaccination with rMenB+OMV NZ.
	
Immune response to rMenB+OMV NZ The immune response to rMenB+OMV NZ when administered with/without MenACWY will be evaluated by measuring bactericidal activity against N. meningitidis serogroup B test strains M14459, 96217, NZ98/254 and M07-0241084 in both MenB+MenACWY and MenB Groups as following:
 
 GMTs at one month after first and second vaccination with rMenB+OMV NZ and Geometric Mean Ratio (GMRs) at one month after the first (Visit 2, Month 1) and the second (Visit 4, Month 3) rMenB+OMV NZ vaccination compared to the baseline at Visit 1, Day 1/Month 0. The percentage of subjects with hSBA titers \geq Lower Limit of Quantitation (LLOQ) for each and all serogroup B test strains, one month after the first (Visit 2, Month 1) and second (Visit 4, Month 3) vaccination. The percentage of subjects with fourfold increase in hSBA titers relative to baseline (Visit 1, Day 1/Month 0) is defined as: 
 For a pre-vaccination titer $<$ limit of detection (LOD), a post-vaccination titer (Visit 2, Month 1 and Visit 4, Month 3) of \geq fourfold the LOD or \geq LLOQ, whichever is greater, For a pre-vaccination titer \geq LOD but $<$ LLOQ, a post vaccination titer (Visit 2, Month 1 and Visit 4, Month 3) of at least fourfold the LLOQ,

CONFIDENTIAL

205419 (MENB REC 2ND GEN-045 (V72_79))

Protocol Amendment 7 Final

Objectives	Endpoints
	
 – For a pre-vaccination titer \geq LLOQ, a post vaccination titer (Visit 2, Month 1 and Visit 4, Month 3) of at least fourfold the pre-vaccination titer (for Groups MenB+MenACWY and MenB). • The ratio of GMTs (rMenB+OMV NZ when administered with MenACWY [Group MenB+MenACWY] versus rMenB+OMV NZ when administered alone [Group MenB]), one month after the first vaccination (Visit 2, Month 1).

To assess the immune response to MenACWY in healthy subjects 16-18 years of age against each of the serogroups A, C, W and Y, at one month after the (study) vaccination with MenACWY.
	
Immune response to MenACWY The immune response to MenACWY when administered with/without rMenB+OMV NZ at baseline (i.e. pre-vaccination, Visit 1, Day 1/Month 0) and at one month after the first vaccination (Visit 2, Month 1; Groups MenB+MenACWY and MenACWY) will be assessed for the serogroups A, C, W and Y as:
 
 • The percentage of subjects with hSBA titers \geq LLOQ, for each serogroup. • GMRs at one month after first vaccination compared to baseline • The percentage of subjects with fourfold increase in hSBA titers relative to baseline (Visit 1, Day 1/Month 0) is defined as: 
 – For a pre-vaccination titer $<$ LOD, a post vaccination titer (Visit 2, Month 1) of \geq fourfold the LOD or \geq LLOQ, whichever is greater, – For a pre-vaccination titer \geq LOD but $<$ LLOQ, a post vaccination titer (Visit 2, Month 1) of at least fourfold the LLOQ, – For a pre-vaccination titer \geq LLOQ, a post vaccination titer (Visit 2, Month 1) of at least fourfold the pre-vaccination titer (for Groups MenB+MenACWY and MenACWY).

[figure not shown]
CCI

*The NHBA indicator strain M07-0241084 may be subject to change during the study before clinical testing starts. In this case, this change will be documented in the clinical report.

The study will be deemed successful if both:

1. the non-inferiority of rMenB+OMV NZ when given concomitantly with MenACWY versus rMenB+OMV NZ alone and
2. the non-inferiority of MenACWY when given concomitantly with rMenB+OMV NZ versus MenACWY alone are demonstrated.

Overall Design (*Amended 11 October 2022*):

Approximately 945 subjects will be screened to achieve 750 evaluable subjects for an estimated total of 250 evaluable subjects per treatment group. Withdrawals will not be replaced.

- Experimental design: Phase IIIB, observer-blind, randomized, controlled, multicentric, study with 3 parallel groups.
- Study groups:
 - Group MenB+MenACWY: rMenB+OMV NZ given concomitantly with MenACWY at study Day 1; rMenB+OMV NZ at study Day 61; Placebo at study Day 91.
 - Group MenB: rMenB+OMV NZ given concomitantly with Placebo at study Day 1 and rMenB+OMV NZ at study Day 61; MenACWY at study Day 91.
 - Group MenACWY: MenACWY given concomitantly with Placebo at study Day 1; rMenB+OMV NZ at study Day 61 and at study Day 91.
- Duration of the study:
 - Epoch 001: Primary starting at Visit 1 (Day 1) and ending at Visit 4 (Day 91)
 - Epoch 002: Safety follow-up period starting at Visit 4 (Day 91) and ending at Study termination-call (Day 451 [Month 15]) *or (Day 271 [Month 9]) for subjects who have not reached Day 271 at the time this amendment takes effect*

2. SCHEDULE OF ACTIVITIES (SOA)

Table 3 Schedule of Activities (Amended 11 October 2022)

Age (years)	16-18 at study start												Notes	
Epoch	Epoch 001						Epoch 002							
Type of contact*	Visit 1	SFU 1	Visit 2	Visit 3	SFU 2	Visit 4	SFU 3	Visit 5	SFU 4	SFU 5*	SFU 6	SFU 7		
Timepoint (s) [refer to Table 4 and Table 5 for visit windows]	Day 1	Day 15	Day 31	Day 61	Day 75	Day 91	Day 105	Day 121	Day 181	Day 271	Day 361	Day 451		
Sampling timepoints	Pre-Vacc I		Post-Vacc I			Pre-Vacc III								
Informed consent	●												Activities that can be performed at a separate visit before Visit 1 (approximately 2 weeks before the Visit 1). AEs / SAEs related to study participation or to a concurrent GSK medication/vaccine should also be recorded starting from this separate visit. Inclusion/exclusion criteria should be re-checked prior to vaccination at visit 1. See Section 12.4.3 for details.	
Check inclusion/exclusion criteria	●			●		●							See Section 6.1 and 6.2 for Inclusion and Exclusion criteria.	
Collect demographic data	●												See Section 8.2.2 for more information.	
Medical history	●												See Section 8.2.3 for more information.	
Medical history-directed Physical examination	○												See Section 8.2.3 and 8.2.4 for more information.	
Symptom-directed physical examination				○		○							See Section 8.2.4 for more information.	
Urine pregnancy test (pre-vaccination)	●			●		●							Only for women of childbearing potential. A pregnancy test is mandatory on Visit 1, Visit 3, and Visit 4 even if performed during a prior separate visit See Section 8.2.5 for more information.	

CONFIDENTIAL

205419 (MENB REC 2ND GEN-045 (V72_79))
Protocol Amendment 7 Final

Age (years)	16-18 at study start											Notes	
Epoch	Epoch 001						Epoch 002						
Type of contact [¥]	Visit 1	SFU 1	Visit 2	Visit 3	SFU 2	Visit 4	SFU 3	Visit 5	SFU 4	SFU 5 [¥]	SFU 6	SFU 7	
Timepoint (s) [refer to Table 4 and Table 5 for visit windows]	Day 1	Day 15	Day 31	Day 61	Day 75	Day 91	Day 105	Day 121	Day 181	Day 271	Day 361	Day 451	
Sampling timepoints	Pre-Vacc I		Post-Vacc I			Pre-Vacc III							
Check contraindications and warnings and precautions to vaccination	●			●		●							See Section 7.7 and 7.8 for more information.
Pre-vaccination body temperature	●			●		●							See Section 8.2.6 for more information.
Vaccines													
Study group and treatment number allocation	O												See Section 7.2.2.1 for more information.
Treatment number allocation for subsequent doses				O		O							See Section 7.2.2.2 for more information.
Recording of administered treatment number	●			●		●							See Section 7.2.2 for more information.
Vaccines administration	●			●		●							See Section 7.1 for more information.
Laboratory Assays													
Blood sampling for antibody determination (~20 mL, at each visit)	●		●			●							Blood sample collection on Visit 1 and Visit 4 will be performed before vaccine administration. See Section 8.3.4.1 for more information.
Safety assessments													
Record any concomitant medications/vaccinations [¥]	●	●	●	●	●	●	●	●	●	●	●	●	See Section 7.5 for more information.
Record any intercurrent medical conditions [¥]	●	●	●	●	●	●	●	●	●	●	●	●	See Section 7.6 for more information.
Distribution of eDiary	O												
Review of eDiary			O			O		O					

CONFIDENTIAL

205419 (MENB REC 2ND GEN-045 (V72_79))
Protocol Amendment 7 Final

Age (years)	16-18 at study start											Notes	
Epoch	Epoch 001						Epoch 002						
Type of contact [¥]	Visit 1	SFU 1	Visit 2	Visit 3	SFU 2	Visit 4	SFU 3	Visit 5	SFU 4	SFU 5 [¥]	SFU 6	SFU 7	
Timepoint (s) [refer to Table 4 and Table 5 for visit windows]	Day 1	Day 15	Day 31	Day 61	Day 75	Day 91	Day 105	Day 121	Day 181	Day 271	Day 361	Day 451	
Sampling timepoints	Pre-Vacc I		Post-Vacc I			Pre-Vacc III							
Return of eDiary							O						
30 minutes post-injection assessment	●			●		●							
Recording of solicited adverse events (Days 1-7 post vaccination) in eDiary	O			O		O							
Recording of unsolicited adverse events within 30 days post-vaccination	●	●	●	●	●	●	●	●					
Recording of unsolicited AEs leading to vaccine/study withdrawal, medically attended AEs, SAEs, pregnancies and AESIs* [¥]	●	●	●	●	●	●	●	●	●	●	●	●	See Section 12.5.8 for more information.
Recording of SAEs related to study participation, or to a concurrent GSK medication/vaccine** [¥]	●	●	●	●	●	●	●	●	●	●	●	●	
Study Conclusion [¥]										●	●	●	See Section 5.4 for more information.

● is used to indicate a study procedure that requires documentation in the individual eCRF.

○ is used to indicate a study procedure that does not require documentation in the individual eCRF.

*COVID-19 infection-related AEs and SAEs should also be recorded on a separate eCRF page.

**Recording of SAEs related to study participation, or to a concurrent GSK medication/vaccine begins from the time a parent(s)/LAR(s) or participant signs the consent form to the end of the study

¥ Safety follow up and contact will terminate at SFU 5 for subjects who have not reached SFU 5 at the time this amendment takes effect. Please note that for these subjects, the termination call would be performed at SFU 5.

Whenever possible, the investigator should arrange study visits within the intervals described in [Table 4](#). For safety follow-up calls, the windows in [Table 5](#) will apply.

Table 4 Intervals between study visits (Amended 11 October 2022)

Interval	Length of interval	Allowed interval
Visit 1 → Visit 2	30 days	23 - 58 days
Visit 1 → Visit 3	60 days	53 - 88 days
Visit 3 → Visit 4	30 days	23 - 58 days
Visit 4 → Visit 5	30 days	23 - 58 days

Table 5 Intervals between study visits and safety follow-up calls (Amended 11 October 2022)

Interval	Length of interval	Allowed interval
Visit 1 → SFU 1	14 days	11 - 17 days
Visit 3 → SFU 2	14 days	11 - 17 days
Visit 4 → SFU 3	14 days	11 - 17 days
Visit 4 → SFU 4	90 days	83 - 111 days
Visit 4 → SFU 5*	180 days	173 - 201 days
Visit 4 → SFU 6	270 days	263 - 291 days
Visit 4 → SFU 7	360 days	353 - 381 days

*Safety follow up will terminate at SFU 5 for subjects who have not reached SFU 5 at the time this amendment takes effect.

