8.2. Pre-vaccination procedures

8.2.1. Data Collected from Subjects

The following data will be collected from each subject over the duration of their study participation:

- Demographic Information.
- Medical history (any significant past diagnoses including allergies, hospitalizations, surgeries requiring in-patient hospitalization, any other medical conditions which may impair the assessment of safety of the rMenB+OMV NZ and MenACWY vaccines).
- Vaccination history as confirmed by vaccination records, if accessible.
- Pre-vaccination body temperature.
- Post-vaccination immediate reactions observed for at least 30 minutes after injection: signs or symptoms of anaphylaxis, allergic phenomena (such as rashes, itching, or other allergic manifestations). Local and systemic solicited data (including e.g., use of medication to treat or prevent fever, and/or pain).
- Post-vaccination solicited local and systemic AEs collected at home by subject and/or subject's parent(s)/LAR(s) and recorded on Subject Diary (eDiary) for 7 days following each vaccination visit.
- Adverse Events.
 - Unsolicited AEs occurring within 30 days after each vaccination will be collected for all subjects by interviewing the subject and/or subject's parent(s)/LAR(s) (as applicable) during the site visits or Safety Follow-up Calls and by reviewing of available medical records.
 - SAEs occurring during the entire study period

- Medically attended AEs occurring during the entire study period
- AEs leading to premature withdrawal from the vaccination/study occurring during the entire study period
- AESI occurring during the entire study period (for subjects who received rMenB+OMV NZ)
- Prior and concomitant medication as defined in Section [7.5](#).

All data collected must only be identified using the GSK Subject ID, as described in Section [7.2](#), documented in the source documents and entered in the eCRF*.

*Only the solicited local and systemic AEs 30 minutes post vaccination are entered in the eCRF. The solicited local and systemic AEs during 7-day post-vaccination period are not entered in the eCRF and are documented only in eDiary.

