8.4.2. Follow-up Clinic Visit

Follow-up clinic visits will be performed on study Days 31 (Visit 2), 91 (Visit 4) and 121 (Visit 5).

During the follow-up clinic visit on study Days 31 (Visit 2), 91 (Visit 4) and 121 (Visit 5), the eDiary will be reviewed by the staff. Study-specific requirements are described in the SPM. At last Follow-Up clinic visit (Day 121), the eDiary should be returned to the study site and collected. For details on the eDiary see Section [12.5.8](#).

The subject and/or parent(s)/LAR(s) will be interviewed to determine if any unsolicited AEs occurred and if any concomitant medications associated with those events or vaccines were taken/received in the time since the last clinic visit. The healthcare professional reviewing these data will discuss the symptoms (if any) reported by the subject and will determine if any additional diagnoses and/or AEs are present. AEs reported by the subject and/or parent(s)/LAR(s) at this follow-up clinic visit must be

recorded in the subject's source document and on an Adverse Events eCRF, as specified in Section 8.4.

Perform a brief symptom-directed physical examination if necessary according to symptoms the subject has reported. This is a physical examination that will include an examination of organ systems that are relevant to the investigator based on review of the subject's reported AEs, concomitant medication use. This assessment may include measurement of vital signs, body temperature (preferably oral) and a check of general appearance. The physical assessment must be performed by the investigator or designee of the investigator, who is qualified to perform a physical assessment in accordance with their institutional policy (see [glossary of terms](#) for definition of a qualified healthcare provider). Any relevant clinical finding (when deemed abnormal) resulting from the symptom-directed physical examination should be documented in the subject's source document and eCRF(s).

Approximately 20 mL of blood will be drawn from all subjects for immunological evaluation at Visit 1 (Day 1), Visits 2 (Day 31) and Visit 4 (Day 91). Refer to Section 8.3.2.

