12.5.3. Solicited adverse events

The term “reactogenicity” refers to solicited signs and symptoms (“solicited adverse events”) occurring in the hours and days following a vaccination, to be collected by the subjects/parent(s)/LAR(s) for 7 consecutive days (with ongoing solicited AEs collected until resolution or day 30, whichever occurs first), using a pre-defined Subject Diary .

The following solicited adverse events are included in the Subject Diary. Each adverse event is to be assessed using the scoring system reported in parentheses below:

The collected data will be entered into the Subject eDiary. Please see Section 12.5.8 for more detail.

a. Solicited local (injection-site) adverse events

The following local (injection-site) AEs will be solicited:

Table 26 Solicited local adverse events*

All age groups
Pain at injection site
Redness at injection site
Swelling at injection site
Induration at injection site

* Solicited local AEs occurring within 30 minutes after vaccination.

b. Solicited systemic adverse events

The following systemic AEs will be solicited:

Table 27 Solicited systemic adverse events

Adolescents (from 11 years of age) and adults
Fatigue
Fever (body temperature $\geq 38.0^{\circ}\text{C}/100.4^{\circ}\text{F}$)
Nausea
Headache
Myalgia
Arthralgia

Note: Subjects/parent(s)/LAR(s) will be instructed to measure and record the body temperature (preferably oral) in the evening. Should additional temperature measurements be performed at other times of day, subjects/parent(s)/LAR(s) will be instructed to record the highest temperature in the eDiary.

The study staff must review the data entered into the Subject Diary as described in Section [12.5.8](#).

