12.5.8.1. Post-vaccination reminders

Reminder calls or alerts are not intended to be an interview for collection of safety data. If the subject/subject's parent(s)/LAR(s) wishes to describe safety information, this information should only be collected by a healthcare professional at the site, and the safety data described must be written down in the subject's medical chart.

12.5.8.1.1. *Subject Diary Alerts*

The subject/subject's parent(s)/LAR(s) will receive daily reminders via the Subject Diary device's in-built audio-visual alarms to alert the user to complete the diary during the post vaccination period, which is from Day 1 though Day 7, after each vaccination visit.

The Subject Diary system will also allow for regular alerts to be issued via email to site staff indicating where subjects may need to be contacted due to:

- Non-compliance (i.e. failing to enter or transmit diary data),
- Reporting of any severe solicited reactions,
- Subject experienced an unsolicited adverse event that required hospitalization or visit to the emergency room or medically attended events that were of concern to the parents/LAR(s).

Sites must assess these alerts when received and contact subjects as necessary. Please refer to Section 5.3 on the premature withdrawals from the study and Section 12.5.8.3 on the evaluation of Adverse Events for guidance on necessary action in the event of one of these alerts.

12.5.8.2. Time period for detecting and recording adverse events, serious adverse events and pregnancies

All AEs during 30 days following administration of each dose of study vaccines must be recorded into the appropriate section of the eCRF, irrespective of intensity or whether or not they are considered vaccination-related.

Any solicited AE that has not resolved within 30 days post vaccination and is reported during clinic visits or safety follow-up calls will be entered into the subject's eCRF as an unsolicited AE. It will also be included in the subject's source documents at the site by the investigator/site staff as a verbally reported event. It will not be included in the Subject eDiary. These AEs will be analysed as unsolicited AEs (i.e. in the Unsolicited Safety Set).

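### Protocol Tables 3 and 4 do not guarantee full observation of the 30-day unsolicited AE window after dose 3: up to 6 of the 30 days can fall after the last scheduled recording contact

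*Protocol*

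**What the plan says.** The primary safety endpoint (Protocol Synopsis and Table 6; SAP section 2) counts subjects with "any unsolicited AEs (including all SAEs), AEs leading to withdrawal and medically attended AEs during the 30 days (including the day of vaccination") after each of the three vaccinations. Dose 3 is given at Visit 4.

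- **Visit window.** Protocol Table 4 gives "Visit 4 → Visit 5" a nominal length of 30 days and an allowed range of 23 to 58 days. SAP Table 3 repeats it. The lead-in reads "Whenever possible, the investigator should arrange study visits within the intervals described in" that table.
- **Schedule of Activities.** The Protocol Table 3 row "Recording of unsolicited adverse events within 30 days post-vaccination" is marked at every contact from Visit 1 to Visit 5 and at none from SFU 4 to SFU 7. The table's legend says that a filled mark means the procedure must be documented in the eCRF. A separate row for SAEs, medically attended AEs, AESIs and AEs leading to withdrawal is marked at every contact.
- **Next contact.** Table 5 puts SFU 4 at 83 to 111 days after Visit 4. SFU 3 falls at 11 to 17 days.
- **Body text.** Section 12.5.8.2 says "All AEs during 30 days following administration of each dose of study vaccines must be recorded". Section 8.2.1 collects 30-day unsolicited AEs by interview "during the site visits or Safety Follow-up Calls and by reviewing of available medical records". Section 8.4.3 has the call script cover unsolicited AEs, and 12.5.4 has them reviewed at the calls too.
- **Diary.** Section 8.4.2: "At last Follow-Up clinic visit (Day 121), the eDiary should be returned to the study site and collected". Section 12.5.3 has solicited AEs collected for 7 days, "with ongoing solicited AEs collected until resolution or day 30, whichever occurs first".

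**The concern.** The allowed Visit 5 interval opens before the 30-day window closes, and the schedule plans no later contact to complete that window. Sections 5.2 and 8 call adherence to the Schedule of Activities essential. A site that follows Table 3 literally would record unsolicited AEs at an early Visit 5 and have no scheduled prompt to ask about the remaining days.

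At stake is the completeness of one component of a primary safety endpoint: any unsolicited AE in the 30 days after the third vaccination. Under-recording would bias that percentage downwards. The SAP (5.5.1.3 and 10.1.2) has no rule for subjects whose window was incompletely observed, so the shortfall would not show in the tables.

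**Working it through.** **Inputs.** Visit 4 on Day 91 (Protocol Table 3); window of 30 days with the vaccination day as day 1 (Synopsis endpoint); Visit 5 at *k* days after Visit 4, with *k* from 23 to 58 (Table 4); SFU 4 at 83 to 111 days after Visit 4 (Table 5).

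**The plan's own figure.** Nominal Visit 5 = 91 + 30 = Day 121, as in Table 3. The allowed range is 91 + 23 = Day 114 to 91 + 58 = Day 149.

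**Window.** First day 91, last day 91 + 29 = Day 120. At the nominal Visit 5 (Day 121) the window is complete.

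**Days after Visit 5.** Uncovered days = 120 − (91 + *k*) = 29 − *k*, and zero once *k* ≥ 29.

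| Visit 5, days after Visit 4 | Study day | Window days after Visit 5 |
|---|---|---|
| 23 | 114 | 6 (Days 115–120) |
| 24 | 115 | 5 |
| 28 | 119 | 1 |
| 29 | 120 | 0 |
| 30 | 121 | 0 |

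The maximum within the allowed interval is 6 of 30 days, 6/30 = 20%. It becomes 7 if the visit day itself is treated as uncovered, or if the vaccination day is left out of the window. At 29 days no whole day is left over; at 30 days the visit falls after the window.

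**Can another contact cover the gap?** SFU 3 is too early (11 to 17 days after dose 3). SFU 4 falls on 91 + 83 = Day 174 to 91 + 111 = Day 202, which is 174 − 120 = 54 to 202 − 120 = 82 days after the window closes.

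**Size of a possible loss.** If a share *p* of subjects attends on the first allowed day and the rest at 29 days or later, onset is uniform over the 30 days and SFU 4 recovers nothing, the fraction of at-risk AEs missed is *p* × 6/30:

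- *p* = 0: 0%
- *p* = 10%: 0.10 × 0.20 = 2%
- *p* = 100%: 1.00 × 0.20 = 20%

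The documents give no Visit 5 timing or onset distribution, so *p* is an assumption and this is a range, not an estimate.

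**The case against.** The strongest reply is that the protocol already requires these events. Section 12.5.8.2 obliges sites to record every AE within 30 days of each dose, and 8.2.1, 8.4.3 and 12.5.4 all bring the follow-up calls in. That stands, and it limits the point. A reader might infer from Table 3 that the 6 days go uncollected, or that SFU 4 records only serious and similar events. The text does not support either: SFU 4 can still pick up the rest, though at 2 to 3 months' recall. What survives is that the body text asks for something that Table 3 does not schedule.

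Three further readings are tempting and should not be drawn:

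- **Diary return loses unsolicited AEs.** Section 12.5.8 says that the diary captures them too, but 8.2.1 and 12.5.4 collect them by interview and record review, so returning the device closes no route. The 7-day solicited period is complete by post-dose day 24. At most, early return shortens diary follow-up of solicited AEs still ongoing.
- **Dose 3 is not comparable with dose 2.** Visit 4 may itself fall 23 days after Visit 3, dose 3 is then given, and SAP 10.1.1 attributes an event to the most recent dose. Dose 2 can be cut at the same point. Only for dose 1 does a later marked contact (Visit 3, at 53 to 88 days) always follow the full window before another dose.
- **The co-administration comparison is compromised.** Both vaccines are given together only at Visit 1, the visit windows are the same in all groups, and safety is descriptive with no between-group tests.

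One check is open: the reporting bars of Protocol Tables 15 and 16 were not legible in the text available, so the statement about scheduled contacts rests on Table 3.

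**Conclusion.** The point holds as a gap in scheduling and an internal mismatch, not as demonstrated data loss. For a subject seen at the earliest permitted Visit 5, 6 of 30 post-dose-3 days (20%) follow the last contact at which Table 3 schedules recording of 30-day unsolicited AEs, and the next contact comes 54 to 82 days after the window closes.

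Exposure is confined to AEs that are non-serious, not medically attended, not AESIs and not a cause of withdrawal, with onset in those days, in subjects attending before 29 days. The loss runs from nothing to 20% of such AEs depending on the unknown attendance pattern, under uniform onset and no recovery at SFU 4; any recovery at SFU 4 lowers it. This is a minor improvement to a primary safety endpoint. It does not affect the immunogenicity conclusions.

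**What to change.** Either of two changes closes the gap:

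1. Set the lower bound of the Visit 4 to Visit 5 interval in Table 4 at 29 or 30 days; 30 days covers the window completely. Visit 5 has no vaccination or blood draw, so nothing else moves. The cost is slightly later bookings.
2. Mark the 30-day unsolicited AE row of Table 3 at SFU 4, restricted to onsets up to day 30 after dose 3. The cost is one table mark and an explicit question in the call script, with recall of 2 to 3 months.

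In both cases, reconcile Table 3 with 8.2.1, 8.4.3, 12.5.4 and 12.5.8.2 so that the schedule and the text name the same contacts.

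If visits are already complete, report by group how many subjects had Visit 5 before the window closed, and add a sensitivity summary of post-dose-3 unsolicited AEs without them. This needs only visit and vaccination dates.
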